#### **7.1.3.3.3 Blood Collection for RNA, Plasma and Serum Biomarker Analysis**

Blood should be collected pre-dose at the timepoints outlined in Section 6.0 – Trial Flow Chart. Leftover RNA, plasma, and serum will be stored at the end of the trial for FBR if the subject has consented (see Section 4.2.3.5).

Further details are provided in the Procedures Manual.

### **7.1.3.4 Planned Genetic Analysis Sample Collection (On-Treatment Tumor Biopsy)**

Sample collection, storage and shipment instructions for Planned Genetic Analysis samples will be provided in the Procedures Manual.

On-treatment tumor biopsy should be performed on Cycle 2 Day 15 (+/- 7 days). Samples will be collected for planned analysis of associations between genetic variants in germline/tumor DNA and drug response.

If a documented law or regulation prohibits (or local IRB/Independent Ethics Committee [IEC] does not approve) sample collection for these purposes, then such samples should not be collected at the corresponding sites.

Leftover DNA extracted from planned genetic analysis samples will be stored for future biomedical research only if subject signs the Future Biomedical Research consent.

### **7.1.3.5 Future Biomedical Research Samples**

The following specimens are to be obtained as part of Future Biomedical Research:

- DNA for future research.
- Remaining RNA.
- Remaining plasma and serum from biomarker analyses.
- Remaining main study tumor.

### **7.1.4 Other Procedures**

#### **7.1.4.1 Withdrawal/Discontinuation**

Subjects who discontinue treatment prior to completion of the treatment regimen should be encouraged to continue to be followed for all remaining study visits.

When a subject discontinues/withdraws from participation in the trial, all applicable activities scheduled for the End of Treatment visit should be performed at the time of discontinuation. Any adverse events which are present at the time of discontinuation/withdrawal should be followed in accordance with the safety requirements outlined in Section 7.2 - Assessing and Recording Adverse Events. .

##### **7.1.4.1.1 Withdrawal From Future Biomedical Research**

Subjects may withdraw their consent for Future Biomedical Research. Subjects may withdraw consent at any time by contacting the principal investigator for the main trial. If medical records for the main trial are still available, the investigator will contact the Sponsor using the designated mailbox ([contact]). Subsequently, the subject's consent for Future Biomedical Research will be withdrawn. A letter will be sent from the Sponsor to the investigator confirming the withdrawal. It is the responsibility of the investigator to inform the subject of completion of withdrawal. Any analyses in progress at the time of request for withdrawal or already performed prior to the request being received by the Sponsor will continue to be used as part of the overall research trial data and results. No new analyses would be generated after the request is received.

In the event that the medical records for the main trial are no longer available (e.g., if the investigator is no longer required by regulatory authorities to retain the main trial records) or the specimens have been completely anonymized, there will no longer be a link between the subject's personal information and their specimens. In this situation, the request for specimen withdrawal cannot be processed.

#### **7.1.4.1.2 Lost to Follow-up**

If a subject fails to return to the clinic for a required study visit and/or if the site is unable to contact the subject, the following procedures are to be performed:

- The site must attempt to contact the subject and reschedule the missed visit. If the subject is contacted, the subject should be counseled on the importance of maintaining the protocol-specified visit schedule.
- The investigator or designee must make every effort to regain contact with the subject at each missed visit (e.g. phone calls and/or a certified letter to the subject's last known mailing address or locally equivalent methods). These contact attempts should be documented in the subject's medical record.

Note: A subject is not considered lost to follow up until the last scheduled visit for the individual subject. The amount of missing data for the subject will be managed via the pre-specified data handling and analysis guidelines

#### **7.1.4.2 Subject Blinding/Unblinding**

This is an open label trial; there is no blinding for this trial.

#### **7.1.4.3 Domiciling**

Subjects will report to the clinical research unit (CRU) prior to dosing on Day 1 of each 21-day cycle to allow for completion of all pre-treatment procedures as outlined in the Trial Flow Chart (Section 6.0).

#### **7.1.4.4 Calibration of Critical Equipment**

The investigator or qualified designee has the responsibility to ensure that any critical device or instrument used for a clinical evaluation/test during a clinical trial that provides important information about inclusion/exclusion criteria and/or safety or efficacy parameters shall be suitably calibrated and maintained to ensure that the data obtained is reliable and/or reproducible. Documentation of equipment calibration must be retained as source documentation at the trial site.

Critical Equipment for this trial includes:

- Laboratory equipment - as required for inclusion laboratory evaluations and trial assessments.
- Imaging equipment – calibration and maintenance of imaging equipment as required for study objectives per local regulations.
- ECG equipment – as required for study assessments.

- Infusion equipment – as required for pembrolizumab administration.
- Refrigerators and freezers – as required to store study treatments and laboratory samples.

Additional guidance regarding critical equipment is provided in the Procedures Manual, Pharmacy Manual, and Site Imaging Manual.

### **7.1.5 Visit Requirements**

Visit requirements are outlined in Section 6.0 - Trial Flow Chart. Specific procedure-related details are provided above in Section 7.1 - Trial Procedures.

#### **7.1.5.1 Screening Visit**

Within 28 days prior to treatment randomization, potential subjects will be evaluated to determine that they fulfill the entry requirements as set forth in Section 5.1. Visit requirements are outlined in the Trial Flow Chart (Section 6.0). Screening procedures may be repeated.

Written consent must be obtained prior to performing any protocol-specific procedure. Results of a test performed prior to the subject signing consent as part of routine clinical management are acceptable in lieu of a screening test if performed within the specified time frame. Screening procedures are to be completed within 28 days prior to the first dose of trial treatment except for the following:

Use the bullets below that apply to the trial.

- Laboratory tests are to be performed within 3 days prior to the first dose of trial treatment. An exception is hepatitis testing which may be done up to 28 days prior to the first dose of trial treatment.
- Evaluation of ECOG is to be performed within 3 days prior to the first dose of trial treatment.
- For women of reproductive potential, a urine or serum pregnancy test will be performed within 72 hours prior to the first dose of trial treatment. If urine pregnancy results cannot be confirmed as negative, a serum pregnancy test will be required (performed by the local trial site laboratory).
- Archival tumor sample collection is not required to be obtained within 28 days prior to the first dose of trial treatment. Newly obtained tumor tissue may be obtained within 90 days of treatment initiation.

Subjects may be rescreened after initially failing to meet the inclusion/exclusion criteria. Results from assessments during the initial screening period are acceptable in lieu of a repeat screening test if performed within the specified time frame and the corresponding inclusion/exclusion criteria is met. Subjects who are rescreened will retain their original screening number.

### **7.1.5.2 Treatment Period Visits**

Visit requirements are outlined in the Trial Flow Chart (Section 6.0). Specific procedure-related details are provided in Section 7.1 – Trial Procedures.

### **7.1.5.3 Post-Treatment Visits**

#### **7.1.5.3.1 End of Treatment – Discontinuation Visit**

The Discontinuation Visit should occur at the time study treatment is discontinued for any reason. If the Discontinuation Visit occurs 30 days from the last dose of study treatment, at the time of the mandatory Safety Follow up Visit, the Discontinuation visit procedures and any additional Safety Follow-up procedures should be performed. Visit requirements are outlined in Section 6.0- Trial Flow Chart. Additional details regarding subject withdrawal and discontinuation are presented in Section 5.7– Subject Withdrawal/Discontinuation.

#### **7.1.5.3.2 Safety Follow-up Visit**

When subjects discontinue study treatment, safety follow-up visit will be required. The Post-Treatment Safety Follow-Up visit should occur approximately 30 days after the last dose of study treatment. If a subject initiates a new anticancer therapy within 30 days after the last dose of study treatment, the Post-Treatment Safety Follow-Up visit should occur before the first dose of the new therapy.

After treatment discontinuation, subjects will be monitored for AEs and SAEs for 90 days. Subjects who initiate new anticancer therapy less than 30 days after study treatment discontinuation will be monitored for AEs/SAEs for 30 days. Subjects who initiate new anticancer therapy between 30 days and 90 days after study treatment discontinuation will be monitored for AEs/SAEs until the day new anticancer therapy is initiated.

Subjects who discontinue treatment for reasons other than confirmed disease progression will have post-treatment follow-up for disease status until disease progression, initiating a new anticancer therapy, withdrawing consent for trial participation, or becoming lost to follow-up, whichever occurs first. Subjects with an AE of Grade > 1 will be followed until the resolution of the AE to Grade 0-1 or until the beginning of a new anti-cancer therapy, whichever occurs first.

#### **7.1.5.3.3 Imaging Follow-up Visits**

Subjects who discontinue treatment for reasons other than verified PD should continue with imaging assessments per the protocol defined schedule until: 1) PD is verified or further confirmed by the investigator, 2) initiation of a new anti-cancer treatment, 3) death, 4) withdrawal of consent or 5) study conclusion or early termination, whichever occurs first.

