Duration of Participation	
Each subject will participate in the trial for up to 28 months from the time the subject signs the informed consent form (ICF) through the final protocol-specified contact.
 
After a screening phase of up to 28 days, each subject will be receiving assigned treatment for up to 24 months. After treatment discontinuation, subjects will be monitored for adverse events (AEs) and serious adverse events (SAEs) for 90 days. Subjects who initiate new anticancer therapy less than 30 days after study treatment discontinuation will be monitored for AEs/SAEs for 30 days. Subjects who initiate new anticancer therapy between 30 days and 90 days after study treatment discontinuation will be monitored for AEs/SAEs until the day new anticancer therapy is initiated. Subjects will be treated until progressive disease, unacceptable toxicity, intercurrent illness that prevents further administration of treatment, investigator's decision to withdraw treatment, subject withdrawal of consent, pregnancy of the subject, noncompliance with trial treatment or procedure requirements, subject completes treatment, or administrative reasons requiring cessation of treatment, at which point they will be discontinued from the study. Upon disease progression, subjects in the monotherapy arm will be able to cross-over to the combination regimen.

Randomization Ratio	N/A

A list of abbreviations used in this document can be found in Section 12.6.

Preladenant will be used throughout the protocol to refer to MK-3814 as supplied by the Sponsor.

Pembrolizumab will be used throughout the protocol to refer to KEYTRUDA® or MK-3475 as supplied by the Sponsor.

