Subjects who discontinue preladenant in monotherapy (Arm 1) due to progressive disease may, at the investigator's discretion and after consultation with the Sponsor, cross-over to the combination treatment (Arm 2) (see Sections 4.2.3.1 and 4.2.3.2). It will be at the discretion of the investigator whether to continue a subject on study treatment until repeat imaging is obtained. Once they discontinue from any part of the study, subjects will be treated at the discretion of the physician.

After treatment discontinuation, subjects will be monitored for AEs and SAEs for 90 days. Subjects who initiate new anticancer therapy less than 30 days after study treatment discontinuation will be monitored for AEs/SAEs for 30 days. Subjects who initiate new anticancer therapy between 30 days and 90 days after study treatment discontinuation will be monitored for AEs/SAEs until the day new anticancer therapy is initiated.

Subjects with an ongoing AE of Grade >1 at the time of treatment discontinuation will be followed until resolution of the AE to Grade 0-1, until considered stable by the treating physician, or until beginning a new anti-cancer therapy, whichever occurs first.

Subjects who discontinue treatment for reasons other than confirmed progressive disease will have post-treatment follow-up for disease status (including imaging) until progressive disease, initiating a new anti-cancer therapy, discontinuing from the study participation, or becoming lost to follow-up.

[figure not shown]
After confirmed progressive disease each subject will be contacted by telephone every 12 weeks (84±7 days) for survival until subject discontinues from the study, becoming lost to follow-up, death, or end of the study, whichever occurs first.

The trial will be conducted in conformance with Good Clinical Practices (GCP).

Specific procedures to be performed during the trial, as well as their prescribed times and associated visit windows, are outlined in the Trial Flow Chart - Section 6.0. Details of each procedure are provided in Section 7.0 – Trial Procedures.

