### 5.2.1.4 Tolerability Evaluation Rules and Dose Escalation

Four dose levels of preladenant are planned in Part 1 ([Table 5](#) and [Table 6](#))

The starting dose (DL1) of preladenant is 25 mg BID. Dose escalation will continue as outlined above (Section 5.2.1.2) according to mTPI dose finding rules.

Table 5 Dose Levels for Preladenant Monotherapy (Part 1: Arm 1)

Arm 1	Preladenant (BID)	
	mg per dose	mg per day
DL-1	10	20
DL1	25	50
DL2	50	100
DL3	100	200
DL4	200	400

Table 6 Dose Levels for Preladenant and Pembrolizumab (Part 1: Arm 2)

Arm 2	Preladenant (BID)		Pembrolizumab (Q3W)
Dose Levels	mg per dose	mg per day	IV Infusion (mg per dose)
DL-1	10	20	200
DL1	25	50	200
DL2	50	100	200
DL3	100	200	200
DL4	200	400	200

Each individual subject will be assigned to a single dose level of study therapy. Intra-subject dose escalation is not allowed. Individual patient dose interruptions and/or dose decreases for preladenant may be implemented based on toxicity as described in Section 5.2.3.1. However, dose adjustments should not be made during the DLT observation period without discussion with the Sponsor. In Arm 2, pembrolizumab administration can be delayed or interrupted but will not be de-escalated see Section 5.2.3.2.

The decision to enroll subjects in the next dose level will be made by the sponsor in consultation with the participating investigators after reviewing the safety and any available PK data of the previous dose level(s).

Subjects may continue on treatment until disease progression, unacceptable toxicity, investigator's decision to withdraw the subject, withdrawal of consent, development of an inter-current condition precluding further administration of study treatment, pregnancy of the subject, failure to comply with dosing evaluations or other study requirements, or administrative reasons requiring cessation of treatment, at which point they will be discontinued from the study.

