9. Adverse events and serious adverse events will be recorded from the time of treatment allocation. All adverse events and serious adverse events that occur after the consent form is signed but before treatment allocation must be reported by the Investigator if they cause the subject to be excluded from the trial, or are the result of a protocol-specified intervention, including but not limited to washout or discontinuation of usual therapy or a study procedure. After treatment discontinuation, each subject will be followed for 90 days for adverse event and serious adverse event monitoring, 30 days if the subject initiates new anticancer therapy less than 30 days after study treatment discontinuation, or the day new anticancer therapy is initiated if between 30 days and 90 days after study treatment discontinuation. Subjects with an ongoing AE of Grade >1 at the time of treatment discontinuation will be followed until resolution of the AE to Grade 0-1, until considered stable by the treating physician, or until beginning a new anticancer therapy, whichever occurs first.
10. Baseline radiology images by CT (or MRI) of chest, abdomen, and pelvis, and all known tumor sites (if evaluable by imaging) must be obtained within 28 days prior to C1D1 and must be repeated every 9 weeks ( $\pm 7$  days) from C1D1 (See SIM). Imaging must be obtained at the End of Treatment visit at discontinuation unless done within the previous 4 weeks. Images are to be submitted to the central imaging vendor for potential future central analysis.
11. After confirmed disease progression subjects will be contacted by telephone every 12 weeks for survival until withdrawal of consent to participate in the study, becoming lost to follow-up, death, or end of the study, whichever occurs first.
12. Tumor tissue (archival or newly obtained biopsy) will be required at Screening upon signing the informed consent for the study. This sample will be assessed to collect information on biomarkers for all subjects enrolled in the study. Tumor tissue will be sent to central laboratory for biomarker analysis and leftover tissue may be saved for future biomedical research (FBR) if the subject signs the FBR consent.

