	Screening Up to 28 days Prior to Day 1 Cycle 1	Treatment Phase						Tumor Assessment	End of Treatment	Post-treatment Follow-Up Phase 		
		Cycle 1			Cycle 2-4		Cycles 5 and all Subsequent Cycles	Every 9 weeks	Discontinuation	Safety Follow-up		Survival Follow-Up 
		Day 1	Day 8	Day 15	Day 1	Day 15	Day 1		At Treatment Discontinuation	30 days after the last dose	90 days after the last dose	Every 12 weeks post discontinuation
Scheduling Window (Days) 	-28 to -1	+3	±3	±3	±3	±3	±3	±7		+7	+7	±7
Administrative Procedures												
Informed Consent 	X											
Informed Consent for Optional Future Biomedical Research 	X											
Inclusion/Exclusion Criteria 	X											
Subject Identification Card 	X											
Medical History 	X											
Prior Oncology Treatment History 	X											
Prior Medications 	X											
Concomitant Medications 	X	X	X	X	X	X	X		X	X		
Clinic Procedures/Assessments												
Physical Examination 	X	X			X		X		X 	X		
12-Lead Electrocardiogram 	X											
Vital Signs 	X	X	X	X	X		X		X	X		
ECOG Performance Status 	X	X			X		X		X	X		
Dispense Preladenant 		X			X		X					
Pembrolizumab infusion 		X			X		X					
Adverse Events Reporting 	X	X	X	X	X	X	X		X	X	X	

Preladenant in Combination with Pembrolizumab (Arm 2 ; Part 1 and Part 2) and (cross-over subjects)												
	Screening Up to 28 days Prior to Day 1 Cycle 1	Treatment Phase						Tumor Assessment	End of Treatment	Post-treatment Follow-Up Phase 		
		Cycle 1			Cycle 2-4		Cycles 5 and all Subsequent Cycles	Every 9 weeks	Discontinuation	Safety Follow-up		Survival Follow-Up 
		Day 1	Day 8	Day 15	Day 1	Day 15	Day 1		At Treatment Discontinuation	30 days after the last dose	90 days after the last dose	Every 12 weeks post discontinuation
Scheduling Window (Days) 	-28 to -1	+3	±3	±3	±3	±3	±3	±7		+7	+7	±7
Tumor Imaging and RECIST 1.1 Response Assessment 	X							X	X			
Survival Status 												X
Laboratory Procedures/Assessments												
Archival or Newly Obtained Tumor Tissue Collection for Biomarker Analysis and Molecular Profiling 	X											
Blood for Genetic Analyses 		X										
Hematology 	X	X	X	X	X	X	X		X	X		

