10. Adverse events and serious adverse events will be recorded from the time of treatment allocation. All adverse events and serious adverse events that occur after the consent form is signed but before treatment allocation must be reported by the Investigator if they cause the subject to be excluded from the trial, or are the result of a protocol-specified intervention, including but not limited to washout or discontinuation of usual therapy or a study procedure. After treatment discontinuation, each subject will be followed for 90 days for adverse event and serious adverse event monitoring, 30 days if the subject initiates new anticancer therapy less than 30 days after study treatment discontinuation, or the day new anticancer therapy is initiated if between 30 days and 90 days after study treatment discontinuation. Subjects with an ongoing AE of Grade >1 at the time of treatment discontinuation will be followed until resolution of the AE to Grade 0-1, until considered stable by the treating physician, or until beginning a new anticancer therapy, whichever occurs first.
11. Baseline radiology images by CT (or MRI) of chest, abdomen, and pelvis, and all known tumor sites (if evaluable by imaging) must be obtained within 28 days prior to C1D1 and must be repeated every 9 weeks ( $\pm 7$  days) from C1D1. Confirmatory imaging are required for all responses (CR and PR) seen by imaging at the study site should be obtained at least 4-5 weeks after the documented response. Imaging must be obtained at the End of Treatment visit at discontinuation unless done within the previous 4 weeks. Images are to be submitted to the central imaging vendor for potential future central analysis.
12. After confirmed disease progression subjects will be contacted by telephone every 12 weeks for survival until withdrawal of consent to participate in the study, becoming lost to follow-up, death, or end of the study, whichever occurs first.
13. Tumor tissue (archival or newly obtained biopsy) will be required at Screening upon signing the informed consent for the study. This sample will be assessed to collect information on biomarkers for all subjects enrolled in the study. Tumor tissue will be sent to central laboratory for biomarker analysis and leftover tissue may be saved for future biomedical research (FBR) if the subject signs the FBR consent.

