#### **7.1.2.6.3 End of Treatment and Follow-up Treatment Imaging**

In subjects who discontinue trial treatment, tumor imaging should be performed at the time of treatment discontinuation ( $\pm$ 4-week window). If a previous scan was obtained within 4 weeks prior to the date of discontinuation, then a scan at treatment discontinuation is not mandatory. In subjects who discontinue trial treatment due to documented disease progression, this is the final required tumor imaging.

In subjects who discontinue trial treatment without documented disease progression, every effort should be made to continue monitoring their disease status by tumor imaging using the same imaging schedule used while on treatment (every 9 weeks) to monitor disease status

until the start of a new anticancer treatment, disease progression, death, or the end of the trial, whichever occurs first.

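### Imaging after treatment stops without progression is required in the text, but Sections 1.0 and 5.2.1.4 discontinue such subjects from the study and the flow charts mark no post-treatment scan, so sites may omit it

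*Combined protocol and SAP*

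**What the plan says.** Five places keep subjects under observation after they stop treatment without progression:

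- Section 7.1.5.3.3: "Subjects who discontinue treatment for reasons other than verified PD should continue with imaging assessments per the protocol defined schedule until" one of five listed events occurs.
- Section 7.1.2.6.3: tumor imaging goes on at the same 9-week interval as during treatment.
- Section 2.1: such subjects have "post-treatment follow-up for disease status (including imaging) until progressive disease" or another listed end point.
- Section 7.1.5.3.2: disease-status follow-up continues when treatment stops for reasons other than confirmed progression.
- Section 5.8.1: stopping treatment is not withdrawal from the trial, and these subjects continue as set out in Sections 6.0 and 7.1.5.

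Two places say otherwise. Section 5.2.1.4 lists reasons for stopping, among them toxicity and investigator decision, and ends: "administrative reasons requiring cessation of treatment, at which point they will be discontinued from the study". Section 1.0 has a similar list, to which it adds completion of treatment, and the same ending: "at which point they will be discontinued from the study".

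In both Section 6.1 flow charts the row "Tumor Imaging and RECIST 1.1 Response Assessment" is marked at Screening, under the 9-week Tumor Assessment heading, and at Discontinuation. The post-treatment phase has 30-day, 90-day and survival columns, none with an imaging mark. The imaging footnotes repeat scans every 9 weeks from C1D1 and add: "Imaging must be obtained at the End of Treatment visit at discontinuation unless done within the previous 4 weeks". The Arm 2 footnote also states: "Confirmatory imaging are required for all responses (CR and PR) seen by imaging at the study site". The Arm 1 footnote has no such sentence.

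**The concern.** A site plans visits from the flow chart and reads the Trial Summary for the outline. Either can lead it to take no scan after the discontinuation visit in a subject who stopped for toxicity, by investigator decision or on completing treatment. A scan that was not taken cannot be recovered at analysis.

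Two kinds of data are exposed. A CR or PR first seen at or shortly before discontinuation needs a second scan at least 4 weeks later to be confirmed under Section 7.1.2.6.2, and the grid gives that scan no visit. Progression after discontinuation would go unobserved, so exploratory PFS and DOR might have to be censored at the last on-treatment scan. ORR is the key secondary endpoint, and the Part 2 futility check turns on whether any response is seen in about 15 subjects.

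**Working it through.** The plan states no figure on this point, so the check sets the passages side by side.

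1. **Does the text end imaging when treatment ends?** Section 7.1.2.6.2 ends it at progression, new anti-cancer treatment, consent withdrawal or death. Section 7.1.2.6.3 lists new treatment, progression, death or end of trial. Section 7.1.5.3.3 lists verified progression, new treatment, death, consent withdrawal or study conclusion. End of treatment is on none of these lists. Section 7.1.2.6.3 calls a scan the final required one only for subjects who stop because of documented progression.

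2. **What does leaving the study trigger?** Section 2.1 names discontinuing from study participation as an event that ends disease follow-up. Read literally, the chain is: stop treatment (1.0, 5.2.1.4), leave the study, disease follow-up ends (2.1). Section 5.8.1 breaks the chain at its first link. The two readings cannot both be followed.

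3. **Where are sites sent for the visit schedule?** Section 5.8.1 sends subjects off treatment to Sections 6.0 and 7.1.5, and repeats that visits in the flow chart should be completed. Section 7.1.5 sends visit requirements back to Section 6.0. Section 7.1.5.3.3 relies on the protocol-defined schedule. The grid at the end of these references marks no post-treatment imaging. Its footnotes run from C1D1 without limiting scans to treatment, but name no post-treatment visit.

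4. **Which responses are exposed?** Take a PR first seen at the scheduled scan on day 63 (9 × 7). Confirmation is possible from day 63 + 28 = 91, or at the next scheduled scan on day 63 + 63 = 126. If the subject stops before day 91, the discontinuation scan is not mandatory, because one was done within the previous 4 weeks, and the grid shows no later scan. If the subject stops on day 91 or later, a discontinuation scan can itself confirm. The exposure is therefore confined to responses first seen at the discontinuation scan or less than 4 weeks before stopping. Under Sections 7.1.2.6.2 and 7.1.2.6.3 the confirmatory scan is still called for in these cases.

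5. **What would one lost response do?** For scale only: Table 15 gives 3/30 = 10% with a 95% CI of 2.1% to 26.5%, and the Clopper-Pearson formula reproduces it. If one of the three were not counted, 2/30 = 6.7% with a CI of 0.8% to 22.1%, a shift of 1/30 = 3.3 points. This assumes that unconfirmed responses are excluded. Section 8.4.1 does not say so, and neither does the futility rule in Section 8.7. It says nothing about how often such a loss would occur.

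**The case against.** The strongest reply is that the protocol already requires these scans, several times over, and that the contrary wording cannot be meant literally. Section 1.0 itself asks for 90 days of adverse-event monitoring after treatment stops, which is impossible for someone out of the study. Section 5.8.1 is the dedicated section on discontinuation, and it points to Section 7.1.5 as well as to the flow chart. Where Section 2.1 speaks of discontinuing study participation, Section 7.1.5.3.2 speaks of withdrawing consent, so the former need not cover stopping treatment. The 9-week column has its own heading, outside the Treatment Phase. The Section 5.2.1.4 list does not include completion of 35 cycles.

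Most of this stands, and it limits the consequence. A reader might infer that late responses cannot be confirmed and that PFS and DOR end at discontinuation. The documents do not support that: Section 7.1.2.6.2 allows confirmation with no on-treatment condition, and PFS and DOR are exploratory, with definitions left to the sSAP. A reader might also take the End of Treatment scan in the footnotes as the last one. The footnotes do not say so; they require it in addition to the 9-week series.

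What the reply does not do is remove the two sentences in 1.0 and 5.2.1.4 or supply the missing column. Much of the protective text also refers the site back to the grid that lacks the visit.

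**Conclusion.** The inconsistency is real and sits in operative text. Sections 1.0 and 5.2.1.4, and both flow-chart grids, are at odds with Sections 2.1, 5.8.1, 7.1.2.6.3, 7.1.5.3.2 and 7.1.5.3.3. The consequence is a risk: post-treatment scans may be omitted at sites that follow the former, leaving some responses unconfirmed and exploratory PFS and DOR censored early.

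The size cannot be derived from the documents. They give no rate of stopping before progression, no expected PFS, no censoring rule and no exclusion of unconfirmed responses from ORR or the futility check, which is itself non-binding. Any figure for bias in PFS would rest wholly on outside assumptions, so none is offered. No sample size, stated probability or confidence interval in the plan changes. The point merits correction because the lost scans would be unrecoverable and the correction is easy.

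**What to change.** Reconcile the passages in two steps.

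- In Sections 1.0 and 5.2.1.4, replace the clause "at which point they will be discontinued from the study" with: *at which point they will be discontinued from study treatment and followed per Sections 5.8.1 and 7.1.5.3*. Subjects who withdraw consent from the trial remain under Section 5.8.2. The reasons for stopping treatment are untouched.
- In both Section 6.1 flow charts, add a post-treatment column, *Imaging Follow-up, every 9 weeks from C1D1*, marked in the tumor imaging row for subjects who stop without progression. Its footnote should include the confirmatory scan of a first CR or PR, already called for in Section 7.1.2.6.2 for all subjects and in the Arm 2 imaging footnote.

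The cost is a wording and flow-chart amendment. It adds no scan beyond those the protocol already calls for and changes nothing in the statistical analysis section.
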